6.7.1.11. Hands, Wrists, and Feet Radiographs

Hands, wrists, and feet radiographs will be taken at the time points indicated in the study procedures table ([Appendix 2](#)). Note that if a subject discontinues the study early and has had X-rays performed in the <12 weeks prior to discontinuation, these do not need to be repeated at ET. Radiographs performed after enrollment may be done +/-7 days of the scheduled visit.

All subjects who discontinue from investigational therapy but continue study visits and procedures, should continue to have radiographs performed as outlined in the study procedure table ([Appendix 2](#)).

The radiographs will be evaluated through central review by 2 independent blinded assessors using the mTSS.

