**Figure 1-1. Study Design**

At Week 24, subjects who have not achieved at least 20% improvement from Day 1 in both swollen joint count (SJC) and tender joint count (TJC) will discontinue investigational study drug dosing but will continue with study visits and assessments per protocol. All subjects meeting this criterion who discontinue from investigational therapy are to receive standard of care treatment for their RA as determined by the investigator.

All subjects who attain responder status at Week 24 will continue on their assigned study drug, in a blinded fashion through Week 52. Placebo-responders at Week 24 will continue on placebo in a blinded fashion through Week 52.

All subjects who have received at least one dose of study drug and exit the study early will complete an early termination (ET) visit at the time of study discontinuation, with a follow up visit four weeks after the last dose of study drug (Post Treatment visit Week 4), regardless of dosing duration.

At completion of the 52-week dosing period all subjects (who did not discontinue assigned study drug or have not met criteria for loss of therapeutic response) will be provided the option to enroll into a separate Long Term Extension (LTE) study (GS-US-417-0304).

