### 3.8.2. Analysis Visit Windows

Subject visits may not occur on protocol-specified days. Therefore, for the purpose of analysis, observations will be assigned to analysis windows.

In general, the baseline value will be the last nonmissing value on or prior to the first dose date of study drug, except for the mTSS baseline value. The mTSS baseline value will be derived based on the measurements collected on or prior to the first dose date of study drug + 14 days given the potential delay in scheduling an x-ray assessment..

For efficacy endpoints, vital signs, electrocardiogram (ECG), weight, lipid, and safety laboratory data, the analysis visit windows will be applied to data collected during the ‘on-treatment’ period. The ‘on-treatment’ period is defined as the last dose date of any study drug plus 7 days.

The analysis windows for on-treatment efficacy endpoints including joint count assessment, HAQ-DI (including subject’s pain assessment), subject’s global assessment (SGA), physician’s global assessment (PGA), serum CRP, CCI [REDACTED] and vital signs, weight, and safety laboratory data (lipid data excluded) are provided in [Table 3-1](#).

**Table 3-1. Analysis Visit Windows for On-treatment Joint Count Assessment, HAQ-DI, SGA, PGA, CRP, CCI [REDACTED] and Vital Signs, Weight, and Safety Laboratory Data (Lipid Data Excluded)**

Analysis Visit	Nominal Study Day	Lower Limit	Upper Limit
Baseline	1	(none)	1
Week 2	15	2	22
Week 4	29	23	43
Week 8	57	44	71
Week 12	85	72	99
Week 16	113	100	127
Week 20	141	128	155
Week 24	169	156	190
Week 30	211	191	232
Week 36	253	233	281
Week 44	309	282	337
Week 52	365	338	≥ 365

The analysis windows for on-treatment ECG data are provided in [Table 3-2](#).

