**Table 3-4. Analysis Visit Windows for On-treatment mTSS Data**

Analysis Visit	Nominal Study Day	Lower Limit	Upper Limit
Baseline	1	(none)	14
Week 24	169	15	267
Week 52	365	268	≥ 365

The analysis windows for on-treatment SF-36, FACIT-Fatigue, EQ-5D and WPAI-RA are provided in [Table 3-5](#). The analysis windows for on-treatment Healthcare Resource Utilization Questionnaire (HRUQ) and Treatment Satisfaction Questionnaire for Medication (TSQM) are provided in [Table 3-6](#).

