## 6. EFFICACY ANALYSES

### 6.1. General Considerations

The primary analysis set for efficacy analyses will be the FAS, defined in Section 3.1.2.

Efficacy analysis will generally be conducted on the following 2 datasets:

- 1) On-treatment data as specified in Section 3.8.2 with exclusion of the observations described as the following. This is the primary analysis dataset for efficacy analysis.

For subjects who continued study drug BUT did not achieve at least 20% improvement from Baseline in both SJC66 and TJC68 at

- Nominal Week 24 visit, then efficacy data collected after nominal Week 24 visit will be excluded from the primary analysis, OR
- Nominal Week 30 visit if subjects missed Week 24 visit or the response status cannot be determined due to missing SJC66 or TJC68 value at Week 24, then efficacy data collected after nominal Week 30 visit will be excluded from the primary analysis

If subjects missed both visits (Week 24 and Week 30) or the response status cannot be determined at both visits, all the efficacy data collected will be included for analysis.

- 2) All available data (including data collected under standard of care).

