## **Missing Data Imputation**

Below are the descriptions for the imputation methods that will be used throughout the efficacy analyses:

- Observed case (OC): Missing values remain missing. For the categorical composite endpoints, in the case that some components are missing, the composite endpoint assessment will be derived based on the non-missing components. If non-missing components are not sufficient to determine final composite endpoint, then the composite endpoint will be set as missing. For continuous composite endpoints (including ACR-N), if any components are missing, the composite endpoints will be set as missing.
- Last observation carried forward (LOCF): Baseline measurements will not be carried forward to postbaseline. Only postbaseline measurements will be LOCF. For the composite endpoints, the last nonmissing postbaseline observation will be carried forward to subsequent visits for each individual component, and then calculate the composite endpoints using individual components imputed by LOCF as described above. If a subject does not have a nonmissing observed record for a postbaseline visit, the last postbaseline record prior to the missed visit will be used for this postbaseline visit. If the last nonmissing observation prior to the missing visits cannot be determined due to multiple measurements occurring at the same time or the time not available within the same day, the worst outcome will be used for LOCF. If missing components still exist after LOCF, the composite endpoints will be calculated using the same rules as described in OC.
- Non-responder imputation (NRI): For all binary response measurements, starting from OC, all missings will be set as non-responders.

If subject only had baseline measurements, LOCF and OC analyses will not include this subject. But this subject will be treated as non-responder in NRI analyses.

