#### **6.4.2. Analysis Methods for Other Secondary Efficacy Endpoints**

The FAS will be used for all summaries and analyses of other secondary efficacy endpoints. Nominal p-values will be presented, if applicable.

The proportion of subjects who achieve ACR20/50/70 and proportion of subjects with change in HAQ-DI  $\geq 0.22$  (ie, reduction in HAQ-DI  $\geq 0.22$ ), DAS28(CRP)  $\leq 3.2$ , and DAS28(CRP)  $< 2.6$  will be analyzed using the the same logistic regression method with NRI as the primary endpoint analysis described in Section 6.2.3. The 2-sided 95% CIs for the proportion based on normal approximation will be provided for each treatment group. The OC and LOCF values will be analyzed as a sensitivity approach to the primary method that uses NRI.

The proportion of subjects having no radiographic progression at Week 24 and 52 will be analyzed using the same logistic regression method based on the OC. Comparison will be made between each filgotinib dose group and MTX alone group. The 2-sided 95% CIs for the proportion based on normal approximation will be provided for each treatment group. In addition, similar analysis will be performed with thresholds of 0 and the smallest detectable change (SDC). The change from Baseline in mTSS, DAS28(CRP), CDAI and SDAI will be analyzed using MMRM method that include all available data at postbaseline visits through Week 52. The MMRM models will include baseline value, stratification factors, treatment, visit, and treatment by visit interaction included as fixed effects and subject being the random effect. An unstructured variance-covariance matrix will be used. The Kenward-Roger method will be used to estimate the degrees of freedom. Missing change scores due to missing study visits or early withdrawal will not be otherwise imputed using the MMRM approach. The LS means along with 95% CIs of the difference in mean change scores from Baseline between each filgotinib dose group and MTX alone group from the MMRM model will be provided for each postbaseline visit. Descriptive statistics of actual and change in DAS28(CRP), CDAI, SDAI, and mTSS from baseline to postbaseline visits will also be performed by treatment and visit.

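### At Week 52, no radiographic progression is tested on observed on-treatment films only, which largely limits the comparison to subjects who passed the Week 24 joint-count criterion

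*SAP*

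**What the plan says.** For the proportion with "no radiographic progression at Week 24 and 52 will be analyzed using the same logistic regression method based on the OC", SAP 6.4.2 compares each filgotinib group with MTX alone. The observed-case rule is defined in SAP 6.1: "Observed case (OC): Missing values remain missing". A subject without a usable film at the visit is therefore not in the model.

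Which films are usable depends on the dataset. SAP 6.1 names on-treatment data, with some further exclusions, and adds: "This is the primary analysis dataset for efficacy analysis". Under SAP 3.8.2 that "period is defined as the last dose date of any study drug plus 7 days". SAP Table 3-4 opens the Week 52 mTSS window at day 268.

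The exit rule is in SAP 1.2 and Protocol 3.2. Subjects who fall short of the joint-count criterion at Week 24 "will discontinue investigational study drug dosing but will continue with study visits and assessments per protocol". If such a subject stays on drug, SAP 6.1 excludes the later efficacy data anyway. Films are still taken after drug is stopped, under Protocol 6.7.1.11: "All subjects who discontinue from investigational therapy but continue study visits and procedures, should continue to have radiographs performed".

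The ACR, HAQ-DI and DAS28(CRP) responder endpoints in SAP 6.4.2 are handled differently: "The OC and LOCF values will be analyzed as a sensitivity approach to the primary method that uses NRI".

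**The concern.** The Week 52 film of a Week 24 joint-count non-responder is collected and read but does not enter the only planned test of this endpoint. Who is left in the test depends on a response seen after randomisation, and the trial expects treatment to change that response. The two sides of the comparison are then no longer the randomised groups, although SAP 6.4.2 assigns these analyses to the FAS. Any structural benefit that comes from having more joint-count responders is conditioned away.

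A single-visit logistic model on observed cases cannot draw on a removed subject's Week 24 film, and no NRI, LOCF, multiple imputation or tipping-point analysis is planned for this proportion. The extra thresholds in SAP 6.4.2 (0 and the smallest detectable change) are not accompanied by any other dataset. Preservation of joint structure at Week 52 is a stated secondary objective, and this is its responder-type readout.

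**Working it through.** **The plan's own figures.** No sample size or power is stated for no radiographic progression. The stated figures reproduce. For mTSS, n per group = 2 × (1.960 + 1.282)² × 2.7² / 0.62² = 399, against 400 stated. For ACR20 at 62% vs 78%, power is 99.9% with 400 vs 400 and 98.3% with 400 vs 200, against over 90% stated.

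**Timing.** Nominal Week 24 is day 169. On-treatment data for a subject who stops then end at about 169 + 7 = day 176. The Week 52 mTSS window opens at day 268, which is 92 days later, so that subject's Week 52 film cannot count.

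**How many are removed.** ACR20 requires a 20% improvement in both joint counts (SAP 6.2.1), so everyone who meets the exit rule is an ACR20 non-responder. The reverse is not true. Let f be the share of ACR20 non-responders who meet the exit rule. The documents do not give f, so it is an assumption, taken as equal in all arms.

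Removed = group size × (1 − ACR20 rate) × f, with ACR20 rates from SAP 1.3:

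| f | MTX alone (400) | Filgotinib 200 mg + MTX (400) | Each other filgotinib group (200) |
|---|---|---|---|
| 100% (upper bound) | 152 (38%) | 88 (22%) | 44 (22%) |
| 50% | 76 (19%) | 44 (11%) | 22 (11%) |
| 25% | 38 (9.5%) | 22 (5.5%) | 11 (5.5%) |

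At the upper bound, 248 vs 312 or 248 vs 156 remain. The imbalance disappears only if f on filgotinib is 38/22 = 1.73 times f on MTX alone. Confirmed loss of response from Week 30 (Protocol 3.2) also ends dosing and can remove further subjects. Those are not counted here.

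**Illustration of the effect.** Assume no-progression of 90% in retained subjects and 70% or 80% in removed subjects, the same in every arm. These rates are not in the documents.

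- 70%, f = 100%: MTX 0.62 × 0.90 + 0.38 × 0.70 = 82.4%; filgotinib 0.78 × 0.90 + 0.22 × 0.70 = 85.6%; difference 3.2 points.
- 80%, f = 100%: MTX 0.558 + 0.304 = 86.2%; filgotinib 0.702 + 0.176 = 87.8%; difference 1.6 points.
- In general the difference is 0.16 × f × (0.90 − rate in removed): 0.8 to 1.6 points at f = 50%, and 0.4 to 0.8 at f = 25%.
- Observed cases: 90% vs 90% throughout, difference 0.

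**Direction.** Within an arm, observed cases overstate the all-randomised rate by (share removed) × (gap between retained and removed). The shift in the filgotinib-minus-MTX difference at f = 100% is 0.22 × gap on filgotinib − 0.38 × gap on MTX. With equal gaps it runs against filgotinib. It would favour filgotinib only if the gap there were more than 0.38/0.22 = 1.73 times the gap on MTX.

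**The case against.** The case against giving this much weight has several parts, and most of them stand.

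- **The endpoint is minor.** It is an other secondary endpoint with nominal p-values, outside the testing hierarchy of SAP 3.5. An on-treatment summary is a legitimate estimand choice. This settles the severity but leaves the comparison without a counterpart on randomised groups.
- **The films are not ignored altogether.** SAP 6.1 defines a second dataset of all available data, and SAP 3.8.2 applies the same visit windows to it. SAP 6.4.2 summarises mTSS value and change on that dataset, and the Week 52 mTSS MMRM partly recovers removed subjects through their Week 24 film. However, the summary is descriptive and does not list this proportion, and no test of it on the second dataset is specified.
- **The illustration is constructed.** It assumes no treatment effect within response groups, so a zero is built in. With 75% in removed subjects, the all-randomised rates are 84.3% and 86.7%. That 2.4-point difference is about one standard error at 400 vs 400: √(0.843 × 0.157/400 + 0.867 × 0.133/400) ≈ 2.5 points.

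Two stronger readings are tempting. One is that 38% and 22% will actually drop out. Those are assumed ACR20 non-response rates. ACR20 can also fail on its other five items, or through missing data under NRI, without meeting the exit rule. SAP 6.1 also keeps all data where joint-count response cannot be determined at both Week 24 and Week 30. The other is that the Week 24 result is equally affected. Those films are taken at or near the exit visit, so Week 24 is largely spared.

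**Conclusion.** The concern holds for Week 52. The planned test is largely limited to joint-count responders, and the documents specify no tested alternative for this proportion. Week 24 removals have an upper bound of 38% on MTX alone and 22% on filgotinib. The actual figure depends on a share that the documents do not give, and on whether that share is similar across arms. The illustrated distortion of 1.6 to 3.2 points at the upper bound rests wholly on assumed progression rates and is smaller at lower shares.

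A reader might infer that the Week 52 structural result is known to be biased in a given direction, or that the trial's formal conclusions are at risk. The documents support neither: progression rates by response status are not stated, and the primary and hierarchical tests do not use this analysis. The point is a cheap improvement of low severity.

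**What to change.** In SAP 6.4.2, add for Week 52 the same logistic regression of no radiographic progression on the second dataset of SAP 6.1, so that all available films count, including those taken under standard of care. Report it beside the on-treatment observed-case result, and tabulate by arm how many subjects the observed-case analysis leaves out.

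The cost is a little more analysis work, with no new visits or data. The drawback is interpretive: a Week 52 film taken after drug was stopped also reflects the standard-of-care treatment received since, and subjects who left the study still have no film.

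Deriving the proportion from imputed mTSS is not proposed as the main remedy. SAP 6.3.3.2 plans that imputation for Week 24 only, and cutting linear-regression draws at 0.5 may be poorly calibrated. For example, with an assumed mean change of 0 to 0.5 and a residual SD of 1.5 (assumed) to 2.7 (the plan's SD), normal draws give 50% to 63% without progression, below the 70-80% assumed above for removed subjects.

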## 6.5. Changes From Protocol-Specified Efficacy Analyses

The following changes were made from the protocol-specified efficacy analyses:

- It has been observed from the blinded data that the enrollment rate is low in some combinations of stratification factors, which will result in a small cell counts for the Cochran- Mantel-Haenszel test adjusted for the stratification factors. The logistic regression analysis with treatment and stratification factors in the model will be used instead to analyze binary endpoints.
- The following two endpoints have been updated as key secondary efficacy endpoints in Section 6.3 and included in the hierarchy testing in Section 3.5, in order to support inclusion in the label.
  - Change from Baseline in SF-36 PCS at Week 24
  - Change from Baseline in FACIT-Fatigue at Week 24
- Given the importance of determining the lowest effective dose for filgotinib in RA, the hierarchical ordering has been updated in Section 3.5 to test filgotinib 100 mg in combination with MTX immediately after each test for filgotinib 200 mg in combination with MTX (including the primary endpoint and each of the key secondary endpoints). In addition, the testing for ACR20, HAQ-DI, and mTSS is moved up earlier in the list to accommodate the changes aforementioned as well as because of the importance of these endpoints in determining drug efficacy in RA. These changes together caused a relative move down for testing of DAS28(CRP)  $<$  2.6.

## **7. SAFETY ANALYSES**

### **7.1. Adverse Events and Deaths**

#### **7.1.1. Adverse Event Dictionary**

Clinical and laboratory adverse events (AEs) will be coded using the MedDRA 21.0. System organ class (SOC), high-level group term (HLGT), high-level term (HLT), preferred term (PT), and lower-level term (LLT) will be provided in the AE dataset.

#### **7.1.2. Adverse Event Severity**

Adverse events are graded by the investigator as Grade 1, 2, 3, 4, or 5 according to toxicity criteria specified in the protocol. The severity grade of events for which the investigator did not record severity will be categorized as “missing” for tabular summaries and data listings. The missing category will be listed last in summary presentation.

#### **7.1.3. Relationship of Adverse Events to Study Drug**

Related AEs are those for which the investigator selected “Related” on the AE CRF to the question of “Related to Study Treatment.” Relatedness will always default to the investigator’s choice, not that of the Medical Monitor. Events for which the investigator did not record relationship to study drug will be considered related to study drug for summary purposes. However, by-subject data listings will show the relationship as missing.

#### **7.1.4. Serious Adverse Events**

Serious adverse events (SAEs) will be identified and captured as SAEs if AEs met the definitions of SAE that were specified in the study protocol. SAEs captured and stored in the clinical database will be reconciled with the SAE database from the Gilead Pharmacovigilance & Epidemiology Department before data finalization.

#### **7.1.5. Treatment-Emergent Adverse Events**

##### **7.1.5.1. Definition of Treatment-Emergent Adverse Events**

Treatment-emergent adverse events (TEAEs) are defined as one or both of the following:

- Any AEs with an onset date on or after the study drug start date and no later than 30 days after permanent discontinuation of study drug
- Any AEs leading to premature discontinuation of study drug

#### 7.1.5.2. Incomplete Dates

If the onset date of the AE is incomplete and the AE stop date is not prior to the first dosing date of study drug, then the month and year (or year alone if month is not recorded) of onset determine whether an AE is treatment emergent. The event is considered treatment emergent if both of the following 2 criteria are met:

- The AE onset is the same as or after the month and year (or year) of the first dosing date of study drug, and
- The AE onset date is the same as or before the month and year (or year) of the date corresponding to 30 days after the date of the last dose of study drug

An AE with completely missing onset and stop dates, or with the onset date missing and a stop date later than the first dosing date of study drug, will be considered to be treatment emergent. In addition, an AE with the onset date missing and incomplete stop date with the same or later month and year (or year alone if month is not recorded) as the first dosing date of study drug will be considered treatment emergent.

#### 7.1.6. Summaries of Adverse Events and Deaths

Treatment-emergent AEs will be summarized based on the Safety Analysis Set.

##### 7.1.6.1. Summaries of AE Incidence in Combined Severity Grade Subsets

The number and percentage of subjects who experienced at least 1 TEAE will be provided and summarized by SOC, HLT, PT, and treatment group. For other AEs described below, summaries will be provided by SOC, PT, and treatment group:

- TEAEs of Grade 3 or higher (by maximum severity)
- TEAEs of Grade 2 or higher
- All TE treatment-related AEs
- TE Treatment-related AEs of Grade 3 or higher (by maximum severity)
- TE Treatment-related AEs of Grade 2 or higher
- All TE SAEs
- All TE treatment-related SAEs
- All TEAEs leading to premature discontinuation of any study drug
- All TEAEs leading to premature discontinuation of study

- All TE SAEs leading to death (ie, outcome of death)
- All TEAEs leading to temporary interruption of any study drug

A brief, high-level summary of AEs described above will be provided by treatment group and by the number and percentage of subjects who experienced the above AEs. All deaths observed in the study will be also included in this summary.

Multiple events will be counted only once per subject in each summary. Adverse events will be summarized and listed first in alphabetic order of SOC and HLT within each SOC (if applicable), and then by PT in descending order of total frequency within each SOC. For summaries by severity grade, the most severe grade will be used for those AEs that occurred more than once in an individual subject during the study.

In addition to the above summary tables, all TEAEs and TE treatment-related AEs will be summarized by PT only, in descending order of total frequency.

In addition, data listings will be provided for the following:

- All AEs, indicating whether the event is treatment emergent
- All AEs of Grade 3 or higher
- All AEs of Grade 2 or higher
- SAEs
- Deaths
- All SAEs leading to death (ie, outcome of death)
- AEs leading to premature discontinuation of any study drug
- AEs leading to premature discontinuation of study
- AEs leading to temporary interruption of any study drug

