3.2. Study Design

This is a randomized, double-blind, placebo- and active-controlled, Phase 3 study in adult male and female subjects with moderately to severely active RA who have limited or no prior exposure to MTX therapy. The study is designed to evaluate the efficacy, safety and tolerability of filgotinib as well as its effect on patient-reported outcomes, including work productivity, fatigue, and quality of life. In addition, PK will be assessed.

Adult male and female subjects with active RA will be screened to determine eligibility as per the inclusion and exclusion criteria (see Section 4.2 and 4.3, respectively). The Screening period will be up to 28 days. The screening window may be extended to up to 42 days prior to the Day 1 visit for subjects who require repeat collection of radiographs.

Written informed consent must be obtained before any study-related procedures take place. During the Screening period, following signing of the informed consent form (ICF), the subject's radiographs (hands, wrists, and feet) will be sent to central review for confirmation of joint erosion (see inclusion criterion 5; Section 4.2). Note that the subject's radiographs need to be sent to central review as soon as possible after completion and prior to Day 1 to allow for central reading and confirmation of one or more joint erosion in subjects that are seronegative.

Subjects will be randomized in a 2:1:1:2 ratio to filgotinib 200 mg plus MTX, filgotinib 100 mg plus MTX, filgotinib 200 mg alone, or MTX alone for up to 52 weeks in a double-blind fashion.

At Week 24, subjects who have not achieved a 20% improvement from Day 1 in both SJC and TJC will discontinue investigational therapy but will continue with study visits and assessments per protocol. All subjects who discontinue from investigational therapy are to receive standard of care treatment for their RA as determined by the investigator.

Responders at Week 24 will continue on the treatment regimens to which they were randomized through Week 52.

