8.6. Safety Analysis

All safety analyses will be performed using the safety analysis set.

Safety will be evaluated by assessment of clinical laboratory tests, physical examinations, vital signs measurements at various time points during the study, and by the documentation of AEs.

All safety data collected on or after the first dose of study drug administration up to 30 days after the last dose of study drug, unless specified otherwise will be summarized by treatment group according to the study drug received.

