##### **7.1.7.1. Adjudication Committee for MACE**

An independent cardiovascular safety endpoint adjudication committee (CVEAC) will be formed to periodically review and adjudicate all potential major cardiovascular adverse events (MACE). MACE is defined as cardiovascular death, nonfatal myocardial infarction and nonfatal stroke.

To identify the MACE, the following potential cases identified using MedDRA search listing (MST) searches will be adjudicated:

- All deaths
- Cardiovascular events (meeting serious criteria)
- Myocardial infarction
- Hospitalization for unstable angina
- Transient ischemic attack
- Stroke
- Hospitalization for cardiac failure
- Percutaneous coronary intervention

The CVEAC will review those potential MACE and related clinical data to determine whether a MACE has developed. The CVEAC's role and responsibilities and the data to be provided to the CVEAC are described in a mutually agreed upon CVEAC charter. The CVEAC charter defines the CVEAC membership, adjudication process, meeting logistics, and meeting frequency. The number and percentage of subjects with positively adjudicated MACE will be summarized by treatment group using the PT term.

A by-subject listing for all patients who have a potential MACE or a positively adjudicated MACE at any time will be provided.

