#### 7.1.7.2. Other Adverse Events of Special Interest

In addition to general safety parameters and MACE, safety information on other adverse events of special interest (AESIs) will also be analyzed. AESIs will be identified by either laboratory results, standardized MedDRA queries (SMQs), or sponsor defined MSTs, or a combination of these methods as indicated below.

- All infections (defined as all PTs in the Infections and Infestations SOC)
- Serious infections (defined as all PTs in the Infections and Infestations SOC that are SAEs)
- Infections of special interest as defined below (identified by using MST)
  - a) Herpes zoster
  - b) Active tuberculosis
  - c) Opportunistic infections
  - d) Hepatitis B or C infections

- Deep vein thrombosis (DVT) and pulmonary embolism (PE) (identified by using MST)
- Malignancy (including lymphoma; not including nonmelanoma skin cancer) (identified by using MST)
- Nonmelanoma skin cancer (identified by MST)
- GI (Gastrointestinal) perforations (identified by MST)

The number and percentage of subjects with aforementioned events of special interest will be provided by the PT term for each AE of special interests.

A by-subject listing for all subjects having AE of special interests at any time will be provided for each AE of special interest.

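### Adverse event tables use crude percentages only, although a response-based stopping rule can give the arms unequal time at risk; first-event rates per patient-year should stand beside them

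*SAP*

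**What the plan says.** **Metric.** SAP 7.1.6.1: "The number and percentage of subjects who experienced at least 1 TEAE will be provided and summarized by SOC, HLT, PT, and treatment group". The counting rule makes this a cumulative proportion: "Multiple events will be counted only once per subject in each summary". SAP 7.1.7.1 does the same for MACE: "The number and percentage of subjects with positively adjudicated MACE will be summarized by treatment group using the PT term". So does SAP 7.1.7.2 for infections, DVT/PE, malignancy and GI perforation: "The number and percentage of subjects with aforementioned events of special interest will be provided by the PT term".

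**Counting window.** SAP 7.1.5.1 requires onset on or after the first dose and "no later than 30 days after permanent discontinuation of study drug", or an event that led to stopping drug. SAP 7.1.7 gives no window of its own for MACE or the other special-interest events. Where nothing else is stated, the default in Protocol 8.6 applies, which covers "All safety data collected on or after the first dose of study drug administration up to 30 days after the last dose of study drug".

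**Stopping rule.** Under Protocol 3.2, subjects without a 20% improvement in both swollen and tender joint counts at Week 24 "will discontinue investigational therapy but will continue with study visits and assessments per protocol". From Week 30, loss of that improvement at two consecutive visits has the same consequence.

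**Exposure.** SAP 4.2.1 tabulates duration of exposure by treatment group, including cumulative counts by week. No adverse event summary uses it as a denominator. Neither document plans a person-time rate, a time-to-event analysis of adverse events, or an adverse event table restricted to the first 24 weeks. SAP 7.7 records no change to the safety analyses.

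**The concern.** A subject who stops at Week 24 leaves the counting window at about Week 28. A subject who continues stays in it until at least Week 52. If the arms differ in response, they differ in average time at risk, and a crude percentage does not take that into account. The rule creates no imbalance before Week 24, so the problem lies in summaries that include later data. These are chiefly the final analysis, and also the Week 24 analysis to the extent that early enrollees contribute follow-up beyond Week 24. SAP 6.1 deals with the Week 24 rule for efficacy data; there is no counterpart for safety. At stake is how far the side-by-side percentages for serious infections, zoster, MACE, DVT/PE and malignancy reflect hazard rather than length of observation.

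**Working it through.** **Plan's own figures.** The documents state no exposure or adverse event rate, so there is none to reproduce. The sample size section, which supplies the response rates used below, does reproduce: 399 per arm against the stated 400 for mTSS (difference 0.62, SD 2.7), with 90.1% power at 400. Power for ACR20 at 62% versus 78% is 99.9% with 400 versus 400 and 98.3% with 400 versus 200, consistent with the stated figure of over 90%.

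**Inputs**
- Planned Week 24 ACR20: 62% on MTX alone, 78% in each filgotinib group (SAP 1.3, Protocol 8.9).
- Stop at Week 24, otherwise dosing to Week 52 (Protocol 3.2, 3.4). Protocol 3.5.2 names Week 14 in its non-responder criterion; that passage and Protocol 3.2 must be reconciled.
- Tail of 30 days = 30/7 = 4.29 weeks (SAP 7.1.5.1).
- Event rates are assumptions: 1, 5 and 100 per 100 patient-years, constant hazard, equal in both arms, 52.18 weeks per year.

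**Step 1: ceiling on the share stopped, s.** ACR20 requires both joint-count improvements plus three of five further items (SAP 6.2.1), and missing data count as failure (SAP 6.2.3). Everyone who fails the joint-count rule also fails ACR20, but not the reverse. So s is at most 1 − 0.62 = 38% on MTX alone and 1 − 0.78 = 22% on filgotinib.

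**Step 2: mean time at risk.** W = (1 − s) × 52 + s × 24 + 4.29.
- MTX alone: 0.62 × 52 + 0.38 × 24 + 4.29 = about 45.6 weeks.
- Filgotinib 200 mg + MTX: 0.78 × 52 + 0.22 × 24 + 4.29 = about 50.1 weeks.
- Ratio 1.10. If completers' windows end at Week 52 (for example on entry to the extension study), 43.0 versus 46.8 weeks, ratio 1.09.

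**Step 3: crude risk at equal hazard r.** Risk = (1 − s)(1 − exp(−r × 56.29)) + s(1 − exp(−r × 28.29)), with r per week. For the rows whose windows end at Week 52, 56.29 becomes 52.

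| Scenario | Rate per 100 PY | MTX alone | Filgotinib 200 mg + MTX | Ratio |
|---|---|---|---|---|
| Ceiling, 38% vs 22% | 1 | 0.87% | 0.96% | 1.10 |
| Ceiling | 5 | 4.27% | 4.68% | 1.10 |
| Ceiling, windows end at Week 52 | 5 | 4.03% | 4.38% | 1.09 |
| Ceiling | 100 | 56.8% | 60.7% | 1.07 |
| Half of ACR20 non-responders stop, 19% vs 11% | 5 | 4.76% | 4.97% | 1.04 |

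A person-time rate ratio would be 1.00 in every row.

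**Step 4: against sampling error.** At the ceiling and 5 per 100 patient-years the artefact is 4.68 − 4.27 = 0.41 points, or 0.0041 × 400 = about 1.6 subjects. The 95% half-width for the difference with 400 per arm is 1.96 × √(0.0427 × 0.9573/400 + 0.0468 × 0.9532/400) = about 2.9 points. At 1 per 100 patient-years the artefact is about 0.3 of one subject.

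**The case against.** The strongest reply is that little follows from this. The adverse event tables are descriptive, with no between-arm test or estimate, and exposure by arm is reported for the same Safety Analysis Set, so a reader can see any imbalance. The ceiling uses a stricter criterion than the actual rule. For the rare events that matter most the artefact is a fraction of a subject. It runs against the sponsor's product, so it hides no filgotinib signal. Person-time rates bring their own distortion: if events cluster early, they dilute the arm followed longer. Deaths are partly covered, because the high-level summary includes all deaths observed in the study, and the MACE and special-interest listings cover events at any time.

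Most of this stands and limits the size of the point. It does not remove it. Mean exposure per arm shows an imbalance but cannot yield person-time censored at the first event for each category. The bias is systematic and does not shrink with sample size.

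A reader might infer that the plan will cause a true excess, or a true lack of difference, to be misread for serious infections, MACE or malignancy. The documents do not support that: even the ceiling is well inside sampling error. Nor do they support taking 1.10 as the expected distortion, or treating the direction as fixed. The lower MTX response is a planning assumption, and the documents give no rates for stopping because of adverse events, withdrawal or later loss of response, which could widen or narrow the gap.

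**Conclusion.** The gap is real and modest. Time at risk is tied to response, and no planned adverse event summary accounts for it. At equal hazard, Week 24 rule-based stopping would raise the crude risk ratio for uncommon events to at most about 1.09 to 1.10 against filgotinib, and to about 1.04 if half of the ACR20 non-responders stop.

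This rests on four assumptions:
- the planned 62% and 78%;
- a similar fraction of ACR20 non-responders failing the joint-count rule in each arm, for which the documents give no figure;
- a constant hazard;
- no other differential stopping.

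The row for all deaths observed in the study has no 30-day cut and is outside this point; treatment-emergent SAEs leading to death are within it. The case is for a cheap addition, not for discarding the crude percentages.

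**What to change.** In SAP 7.1.6.1 and 7.1.7, add subjects with a first event per 100 patient-years at risk, with 95% CI, beside the number and percentage. Do this for treatment-emergent SAEs, treatment-emergent SAEs leading to death, adjudicated MACE and each event of special interest. Define person-time from first dose to the earliest of first event, last dose plus 30 days, data cutoff, or entry to the extension study. State that window in SAP 7.1.7, where none is given now.

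Apply this at the final analysis. The Week 24 analysis can include later follow-up: SAP 4.2.1 runs exposure to the data cutoff for subjects still on drug, and SAP 7.2 takes all laboratory data available at the snapshot. For that analysis, either add the same rates or restrict the adverse event table to events through Week 24. Record the addition in SAP 7.7.

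The inputs, dosing dates and event onset dates, are already collected. The cost is some extra columns and slightly longer output. Because the rates assume a roughly constant hazard, they should be read alongside the crude percentages and not replace them. Trial conduct, the efficacy analyses and the testing hierarchy are unaffected.
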